4.3 Schedule of Activities

5. Statistical Methodology and Study Endpoints

5.1 Statistical and Analytical Plans

Statistical analyses will be conducted using

5.1.1 Common Conventions

5.1.1.1 Analysis Populations

The analysis populations will consist of subjects as defined below:

Table 5-1 Analysis Populations

Population	Definition	Analysis Treatment
Screened	All screened subjects who signed the informed consent	_
Intent-to-Treat (ITT)	All randomized subjects	Actual treatment received
Modified Intent-to- Treat (mITT)	All randomized subjects who received treatment with cannula on 1 cheek and treatment with needle on the contralateral cheek	Actual treatment received
Per Protocol (PP)	All mITT subjects who did not have any significant protocol deviations that could affect the primary endpoint and who received each assigned treatment on the assigned side. A significant deviation that occurred after the primary endpoint would not lead to exclusion from the PP analysis.	Actual treatment received (identical to as randomized, by PP definition)
Safety	All randomized subjects who received ≥ 1 study treatment	Actual treatment received

Analyses of safety variables will be performed on the safety population. Unless specified otherwise, all other analyses will be performed on the mITT population. The PP population will be used to perform PP sensitivity analyses for the primary and secondary effectiveness variables.

Analyses will be based on treatment received, regardless of randomization assignment (ie, "as treated" rather than "as randomized"), in order to prevent bias towards study success (non-inferiority) that would be due to randomization errors that reverse the direction of the paired comparison. In addition, the mITT population will be used to do an "as randomized" sensitivity analysis for the primary effectiveness variable. That will not be necessary for the PP population, since it will exclude subjects who were not treated as randomized.

5.1.1.2 Study Treatments

The following paired-comparison treatments are defined for this study:

- Study Treatment: JUVÉDERM VOLUMA® XC injectable gel using cannula
- Control Treatment: JUVÉDERM VOLUMA® XC injectable gel using needle

5.1.1.3 Statistical Methodology Types

The methodologies defined below apply as specified to individual endpoints defined in this SAP.

5.1.1.4 Missing Data

If there are any mITT subjects with missing scores for the primary effectiveness endpoint, the following 2 missing-data handling methods are pre-specified to use for missing-data sensitivity analysis of the primary effectiveness endpoint. For each method, there will be no missing baseline MFVDS, because protocol inclusion criteria 2 requires a score of 3, 4 or 5.

Table 5-3 Missing Data Handling by Endpoint Type

Endpoint type	Timing	Missing Data Handling
Categorical Response	Month 1	 All subjects included (mITT population) Multiple imputation (eg, via SAS procedure MI) within treatment, with 5 imputed datasets, will be applied to subjects with missing post-baseline MFVDS scores, using the following model: Month 1 MFVDS = β₀+β₁ Baseline MFVDS + β₂ Month 3 MFVDS
Categorical Response	Month 1	 All subject included (mITT population) Baseline observation carried forward (BOCF) for subjects
1		with missing post-baseline MFVDS values.

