8.3 Hypothesis and Methods of Analysis

8.3.1 Primary Effectiveness Analyses

For the primary effectiveness analysis of change from baseline at Month 1 in EI-assessed overall MFVDS, the mean paired difference between treatment with cannula and treatment with needle, and its 95% CI based on the paired t-test will be calculated. If the upper confidence limit is less than 0.5, statistical non-inferiority will be concluded.

If there are any mITT subjects with missing scores for the primary effectiveness endpoint, the following 2 missing-data handling methods are pre-specified to use for missing-data sensitivity analysis of the primary effectiveness endpoint.

- 1) Multiple imputation [REDACTED]

- 2) Baseline observation carried forward (BOCF) to replace missing Month 1 scores

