4.1.1 Overall Design

This is a prospective, multicenter, evaluator-blind, randomized, within-subject, controlled, paired-comparison study of the safety and effectiveness of VOLUMA XC injectable gel using a cannula versus needle for cheek augmentation to correct age-related volume deficit in the midface.

Subjects eligible for study enrollment should have cheeks that are either moderate for both cheeks, significant for both cheeks or severe for both cheeks, as assessed by the EI using the 6-point photonumeric Mid-Face Volume Deficit Scale (MFVDS), ranging from 0-5 (0 = none, 1 = minimal, 2 = mild, 3 = moderate, 4 = significant, 5 = severe).

Eligible subjects will be randomized to undergo treatment with cannula in the right or left cheek and with needle in the other cheek (ie, treatment groups will be "cannula left and needle right" or "needle left and cannula right). Prior to randomization, the subjects' demographic information and cosmetic, medical, surgical and dental history will be recorded. Physical measurements and vital signs will be collected, and a urine pregnancy test will be conducted for women of childbearing potential.

The Treating Investigator (TI) and subject will not be blinded to treatment assignment. The Evaluating Investigator (EI) is to remain blinded to treatment assignments for each cheek throughout the duration of the study. Hence, this is considered to be a single-blind study, although some measurement variables are unblinded (eg, injection ease rated by the treating investigator and procedural pain rated by the subject).

diary for 30 days after the treatment session beginning on the day of treatment. Subjects will

return 1 month after treatment, and the TI will evaluate the treatment areas for localized reaction and will review the safety diary with the subject and discuss reported symptoms.

Subjects will attend follow-up visits for safety and effectiveness at Months 1 and 3 after treatment. Safety and effectiveness assessments will be performed at posttreatment follow-up visits. The EI will rate subjects on the MFVDS for each cheek, the TI (or designee other than EI) will record any adverse events (AEs), and subjects will complete the Satisfaction with Cheeks module of the FACE-Q questionnaire. At the month 3 visit, a urine pregnancy test will be performed for female subjects of childbearing potential. Subjects will be exited from the study at the Month 3 visit after study procedures are completed.

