5.1.1.5 Site Pooling

The impact of investigational sites (not investigator, but site) on the primary effectiveness analysis at Month 1 will be evaluated by ANOVA modeling of the treatment difference in MFVDS score change from baseline as a function of investigational site. Investigational sites with fewer than 6 enrolled subjects will be pooled with other such sites.

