5.1.3.1 Primary Effectiveness Analysis

For the primary effectiveness analysis of change from baseline at Month 1 in EI-assessed overall MFVDS, the mean paired difference between treatment with cannula and treatment with needle,

and its 95% CI based on the paired t-test will be calculated. If the upper confidence limit is less than 0.5, statistical non-inferiority will be concluded.

[figure not shown]

Table 5-15 Primary Effectiveness Analyses

Endpoint	Description	Timing	Methodology		
MFVDS change from	Compare mean difference in the	Baseline and change	Continuous		
baseline to month 1	MFVDS change from baseline score	from baseline to	descriptives with		
	between cannula and needle at Month	months 1	paired-comparison		
	1,		CI		

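### The multiple-imputation sensitivity analysis imputes each cheek on its own, so its interval for the paired difference is too wide when the two cheeks are positively correlated

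*SAP*

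**What the plan says.** Table 5-3 in SAP 5.1.1.4 states: "Multiple imputation (eg, via SAS procedure MI) within treatment, with 5 imputed datasets, will be applied to subjects with missing post-baseline MFVDS scores". The model printed there is "Month 1 MFVDS = β₀+β₁ Baseline MFVDS + β₂ Month 3 MFVDS". It has one outcome, two predictors from the same treatment side, no score from the other cheek and no subject term.

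The analysis to be repeated on the imputed data is that of SAP 5.1.3.1: "the mean paired difference between treatment with cannula and treatment with needle", with a paired-t 95% confidence interval. The decision rule is "If the upper confidence limit is less than 0.5, statistical non-inferiority will be concluded".

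Two design features in SAP 4.1.1 matter here. Eligible cheeks are "either moderate for both cheeks, significant for both cheeks or severe for both cheeks", so the two baselines are equal. At follow-up visits, "The EI will rate subjects on the MFVDS for each cheek", so both Month 1 scores come from one visit.

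Imputation is for sensitivity analysis only (Protocol 8 and 8.3.1). The second method is baseline carried forward. The protocol's own imputation detail is redacted.

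**The concern.** The primary analysis is efficient because the two cheeks share a face, a rater and a visit, and what they share drops out of the difference. An imputation run one side at a time has no means of reproducing that sharing. When a subject misses Month 1, the plan draws two unrelated residuals and subtracts them, so the imputed differences are noisier than real ones. This inflates the variance within each completed data set and the variance between them.

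A missing-data sensitivity analysis should show what the missing scores do to the conclusion. This one adds width that comes from the imputation model. If its upper limit crosses 0.5 when the observed-data limit does not, readers will attribute that to missing data, although part of it is an artefact.

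**Working it through.** **Inputs.** From the documents: n = 60 treated (Protocol 5.1), 5 imputations and the model above, paired-t 95% interval, margin 0.5. Not in the public text, so assumed: missing share f (5, 10, 20%), residual correlation r, and the SDs. The plan gives no figure of its own to reproduce on this point.

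**Step 1: one imputed difference.** Let s² be the residual variance per cheek. A real difference has variance s² + s² − 2rs² = 2s²(1−r). Two independent draws give 2s².

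**Step 2: Rubin's variance** (both cheeks missing in share f, no Month 3 score, many imputations).

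- Within: (2s²/n)[(1−f)(1−r) + f] = (2s²/n)[(1−r) + fr]
- Between: (2s²/n)·f/(1−f)
- Reported total: (2s²/n)[(1−r) + fr + f/(1−f)]
- True variance of the estimate: (2s²/n)(1−r)/(1−f)
- Excess: (2s²/n)·r·[f + f/(1−f)]

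The excess is positive exactly when r > 0, zero at r = 0 and negative when r < 0. If only one cheek is missing it is 2frs²/n, with the same sign.

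Example, f = 0.10 and r = 0.5: the reported bracket is 0.5 + 0.05 + 0.111 = 0.661 and the true one is 0.5/0.9 = 0.556, so the SE ratio is √(0.661/0.556) = 1.09. With 5 imputations the between part is multiplied by 1.2. Against joint imputation the ratio is then √[(0.5 + 0.05 + 0.133)/(0.5 × 1.133)] = √1.206 = 1.10.

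SE ratio, cheek-by-cheek to joint, 5 imputations:

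| f | r = 0.3 | r = 0.5 | r = 0.8 |
|---|---|---|---|
| 5% | 1.02 | 1.05 | 1.19 |
| 10% | 1.04 | 1.10 | 1.35 |
| 20% | 1.08 | 1.18 | 1.59 |

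**Step 3: do the covariates repair it?** Baseline is the same grade on both cheeks, so it says almost nothing about their difference (only the gap between two separately fitted slopes, times baseline). It cannot carry the same-visit correlation that remains. Month 3, when observed, carries part of it.

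**Step 4: simulation.** n = 60, Bayesian regression imputation, m = 5, Rubin's rules with small-sample degrees of freedom, both cheeks missing at random, paired-difference SD 0.6, same-visit correlation 0.5 or 0.7. Excess half-width over joint imputation:

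| Scenario | Correlation | f = 5% | 10% | 20% |
|---|---|---|---|---|
| Month 3 observed, shared visit effect | 0.5 (r = 0.38) | +4% | +7% | +12% |
| | 0.7 (r = 0.60) | +9% | +17% | +31% |
| Month 3 observed, no shared visit effect | 0.5 (r = 0.13) | +3% | +5% | +8% |
| | 0.7 (r = 0.10) | +4% | +7% | +13% |
| Month 3 also missing | 0.5 | +6% | +12% | +21% |
| | 0.7 | +13% | +26% | +44% |

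In grades at 10% missing, joint against cheek-by-cheek half-widths were 0.166 and 0.177, 0.168 and 0.195 (Month 3 observed, visit effect), then 0.168 and 0.187, 0.167 and 0.211 (Month 3 missing). The upper limit therefore rises by 0.011 to 0.044 grade. Coverage was 0.958–0.981 cheek-by-cheek and 0.943–0.957 joint. Mean bias was at most 0.004. One-sided error at the margin (visit-effect scenarios) was 0.7–1.7% against 2.0–2.6%.

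On scores rounded to whole grades, the excess at 10% missing was +5% and +12% (Month 3 observed) and +7% and +18% (Month 3 missing). A repeat gave +6%, +12%, +9% and +20%.

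A separate set of runs with per-cheek residual SD 0.7 and r = 0.3, 0.5, 0.8 gave width ratios at 10% missing of 1.05, 1.12, 1.42 (Month 3 missing) and 1.03, 1.08, 1.30 (observed). At r = 0 the ratio was 1.00.

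**Step 5: the margin.** Trials that passed on observed data but failed under cheek-by-cheek imputation: at true difference 0, at most 0.1% with 5–10% missing and up to 2% with 20%. At true difference 0.25 and 10% missing, 7–14% (Month 3 observed) or 11–21% (missing), against 3–4% under joint imputation.

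**The case against.** The strongest reply concerns weight, not algebra. The primary paired-t analysis uses no imputation and the baseline-carried-forward analysis is unaffected. The flaw touches one sensitivity analysis, and only if Month 1 scores are missing. It over-covers and does not create false non-inferiority.

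Missingness is probably low: one treatment, an endpoint at one month, and a Day 2 to 61 window that also accepts unscheduled visits. About 5% (3 of 60) is a fair central case and 20% a stress case. MFVDS takes whole grades, and on rounded scores the excess is smaller: a further simulation with a shared visit effect gave +3 to +10% at 5% missing and +6 to +18% at 10%.

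The pass-to-fail figures depend on cannula being truly 0.25 grade worse, which nothing in the documents suggests. In that setting the observed-data analysis itself passed only 68–77% of the time. At 5% missing and a true difference of 0.1, 0–1.4% of trials flipped, against 0.3–0.4% when the difference was imputed directly. In the runs with residual SD 0.7, the share meeting the margin fell by at most about 3 points.

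Finally, r is unknown, and further imputation detail may lie in redacted or unavailable text (Protocol 8.3.1, SAP 5.1.1.3).

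All of this limits the consequence and stands. It does not remove the mismatch: the model printed in Table 5-3 has no link between cheeks, the analysis is paired, and positive r is plausible for two cheeks of one face rated by one evaluator at one visit.

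**Conclusion.** The concern holds. As printed, Table 5-3 gives an interval that is too wide whenever the residual between-cheek correlation is positive and Month 1 scores are missing. Under the Step 4 assumptions, at 5–10% missing, the excess is about 3 to 26% on continuous scores. It would be larger with stronger correlation (SE ratio 1.35 at r = 0.8 and 10% missing) and zero at r = 0. If r were negative the interval would be too narrow (SE ratio 0.96–0.99 at r = −0.3).

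The practical effect is mostly confined to results near the margin. With a true difference of zero and at most 10% missing, the conclusion would almost never change. It is a specification error worth correcting in a sensitivity analysis; it does not threaten the primary conclusion. The sizes rest on assumed correlation, SD and missing share, and on the SAP model as printed.

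**What to change.** Rewrite the multiple-imputation row of Table 5-3. Use one record per subject, with no separation by treatment, and impute the cannula-side and needle-side Month 1 scores jointly from baseline and both sides' Month 3 scores. One baseline term is enough because the two grades are equal. Apply the paired analysis to each completed data set and combine by Rubin's rules.

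Imputing the paired difference directly is an acceptable alternative. In simulation it gave nearly the same interval (0.165 against 0.166, and 0.166 against 0.168, at 10% missing with Month 3 observed and a visit effect). The joint form has the advantage of keeping the observed score when only one cheek is missing. The SAP already treats the per-subject difference as an analysis variable in 5.1.1.5: "ANOVA modeling of the treatment difference in MFVDS score change from baseline as a function of investigational site".

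More than 5 imputations is optional; it reduces Monte Carlo noise but does not cure this problem. The cost is one line of SAP text and a small programming change before database lock, with no new data.

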5.1.1.5 Site Pooling

The impact of investigational sites (not investigator, but site) on the primary effectiveness analysis at Month 1 will be evaluated by ANOVA modeling of the treatment difference in MFVDS score change from baseline as a function of investigational site. Investigational sites with fewer than 6 enrolled subjects will be pooled with other such sites.

5.1.2 Demographics and other Baseline Descriptions

5.1.2.1 Analysis Populations Distributions

The distribution of subjects within the analysis populations will be summarized as follows:

Table 5-4 Analysis Population Summaries

Population	Description	Timing	Methodology
Screened	Distribution of All Randomized, Randomized but Discontinued Before Treatment, Unrandomized, Reason not Randomized	Screening period	Categorical counts
Unrandomized	List unrandomized subjects with reasons not randomized	Screening period	Listing
ITT, mITT, PP and Safety	Distribution in total and, for the safety population, if not all treated subjects receive each of the paired treatments, by treatment group	After randomization	Categorical counts

5.1.2.2 Subject Disposition

Subject disposition encompasses the distribution of subjects who enter, complete, and discontinue during each specified analysis period, along with eCRF-reported discontinuation reasons from each respective analysis period. Subject disposition will be summarized as follows:

Table 5-5 Subject Disposition Summaries

Endpoint	Description	Timing	Methodology
Study disposition	Distribution in the randomized (ITT)	Month 1 and final	Categorical counts
	subjects in total		

5.1.2.3 Protocol Deviations

Protocol deviations will be defined in a separate document, including importance classification. Protocol deviations will be summarized as a data listing, as follows:

Table 5-6 Protocol Deviation Summary

Endpoint	Description	Timing	Methodology
Significant protocol	Significant protocol deviation will be listed		listing

Endpoint	Description	Timing	Methodology
deviations			

5.1.2.4 Demographics

Demographics will be summarized for the mITT population in total as follows:

Table 5-7 Demographic Summaries

Endpoint	Description	Timing	Methodology
Age	Age (years) at informed consent date	Informed consent	Continuous descriptives
Age group	 < 40 years 40-65 years ≥ 66 years (none expected) 	Informed consent	Categorical counts
Sex, race, and ethnicity	 eCRF categories Race group White Black or African American Asian American Indian or	Screening Period	Categorical counts

5.1.2.5 Baseline Characteristics

Baseline characteristics will be summarized in total for the mITT population and, if it differs, the safety population as follows:

Table 5-8 Baseline Characteristics Summaries

Endpoint	Description	Timing	Methodology
Baseline characteristics	Height (m)	Latest assessment	Continuous
	• Weight (kg)	prior to	descriptives
	 Body mass index (BMI) 	randomization	
	• Weight (kg) / height (m) ²		
	 Body mass index (BMI) category 		
	$(<18.5, 18.5 - <25, 25 - <30, \ge 30)$		
	 Fitzpatrick skin phototype 		
	(I, II, III, IV, V and VI)		

5.1.2.6 Medical History

Medical history, encompassing abnormalities and surgeries reported as occurring before the Screening Visit, will be coded using the Medical Dictionary for Regulatory Activities (MedDRA), version 20.0 or newer. Unique subjects who report medical history events will be presented in a subject data listing for the ITT population.

Table 5-9 Medical History Summary

Endpoint	Timing	Methodology
Abnormalities and surgeries	Screening Period	Listing
occurring before the Screening Visit		

5.1.2.7 Prior and Concomitant Medications

Medications will be coded using the MedDRA, version 20.0 or newer. The MedDRA system organ class (SOC) and preferred term (PT) will be displayed for the indication, and the preferred name will be displayed as assigned to the 11-digit drug code from the WHO Drug Dictionary Enhanced (DDE). Unique subjects who reported medications will be presented in a subject data listing for the ITT population.

Table 5-10 Medication Summaries

Endpoint	Description	Timing	Methodology
Prior medications	Medications taken before the study treatment start date and time, regardless of medication end date	Screening Period, prior to treatment	Listing
Concomitant medications	Medications taken on or after the study treatment start date and time, regardless of medication start date	Treatment Follow-up period	Listing

5.1.2.8 Exposure to Study Treatment

Treatment exposure related variable will be summarized for safety population by treatment group as follows.

Table 5-11 Exposure to Study Treatment

Endpoint	Description	Timing	Methodology
Volume injected	By cannula, by needle, and combined across cannula and needle separately for each of cannula and needle cheeks	Treatment period	Continuous descriptives

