
STUDY DESIGN: This is a multicenter, evaluator-blind, randomized, within-subject controlled, paired-comparison study of the safety and effectiveness of VOLUMA XC injectable gel using a cannula and needle for cheek augmentation to correct age-related volume deficit in the mid-face.
 
At screening, after written informed consent has been obtained, the Treating Investigator (TI) will document the subject's demographics, Fitzpatrick skin phototype, height, weight, vital signs, and medical, surgical, cosmetic, and dental procedures history. Female subjects of childbearing potential will undergo urine pregnancy testing. All subjects will complete the validated 5-item Satisfaction with Cheeks module of the FACE-Q questionnaire. The blinded Evaluating Investigator (EI) will rate the subject's mid-face deficit for the overall mid-face area, [REDACTED] on the validated 6-point photonumeric Mid-Face Volume Deficit Scale (MFVDS) (0 = none, 1 = minimal, 2 = mild, 3 = moderate, 4 = significant, 5 = severe) to determine eligibility for the study.
 
On the randomization/treatment day, subjects will have 1 cheek treated with VOLUMA XC injectable gel using a [REDACTED] cannula and the contralateral cheek treated using a [REDACTED] with a goal to achieve at least a 1-grade improvement. In the cheek randomized for cannula use, a maximum treatment with cannula should be attempted. [REDACTED]
 
[REDACTED] The side of treatment (ie, side of face for needle or cannula) will be randomized. The left side of face will be treated first for all subjects. For the cheek treated with cannula, an anesthetic agent must be used on the treatment area prior to making the entry point with the introductory needle; use of anesthesia is optional for the cheek treated with needle only. The TI will inject VOLUMA XC in the mid-face to correct mid-face volume deficit. [REDACTED]
 
[REDACTED]
 
At 1 and 3 months after treatment, subjects will return for a visit during which the EI will rate subjects on the MFVDS for the overall mid-face area, [REDACTED] the TI will record any adverse events (AEs), and subjects will complete the Satisfaction with Cheeks module of the FACE-Q questionnaire. Subjects will be exited from the study at the end of the Month 3 visit.

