4.3 Treatment Groups and Treatment Regimen

4.3.1 Study Treatment

VOLUMA XC injectable gel injected with a [REDACTED] cannula and an optional [REDACTED]

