4.3.3 Methods for Blinding

The Evaluating Investigator (EI) will be blinded to treatment. The EI will not be present during the injection procedures. The Treating Investigator (TI), study coordinator, and subject will not be blinded to treatment, but they will secure the randomization and other records (eg, records of study treatments and prior study assessments) from potential discovery by the blinded EI. The TI will not discuss the randomized treatment assignments with or in the presence of the EI.

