8.4 Subgroup Analyses

The primary effectiveness endpoint will be summarized by baseline overall MFVDS score and investigational site. Details will be provided in the statistical analysis plan.

[REDACTED]

Approval Date: 19-Oct-2017

[REDACTED]

[REDACTED]

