9.1.3 Treatment Regimen Adjustments

The TI will determine the appropriate volume of VOLUMA XC to inject based on his/her clinical experience, [REDACTED]

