4.2 Study Objectives and Endpoints

The objective of this study is to evaluate the safety and effectiveness of VOLUMA XC injectable gel using cannula in subjects seeking correction of age-related volume deficit in the mid-face.

The study primary objective, secondary objective, and other objectives are presented with corresponding endpoint(s) below:

Table 4-1 Study Objectives and Corresponding Endpoints

Objectives	Endpoints	
To evaluate the safety and effectiveness of cannula versus needle for the correction of age-related volume deficit in the mid-face.	Primary Endpoint: • MFVDS response distribution by treatment, based on EI assessment on a 6-point scale of ordinal categories, from 0 to 5 (none, minimal, mild, moderate, significant, severe), for baseline and change from baseline to month 1 (primary endpoint)	
	 MFVDS responder rates by treatment, based on EI assessments on a 6-point scale of ordinal categories, from 0-5 (none, minimal, mild, moderate, significant, severe), with responders defined as ≥1 grade improvement from baseline, for month 1 (primary measurement time) Subject's FACE-Q Satisfaction with Cheeks, at the subject level rather than by treatment (because the questions are asked regarding the face rather than the treatment sides), for the 	

FACE-Q Rasch transformed score (0-100), which is converted from the sum score (range 5-20) across 5 items (symmetric, smooth, attractive, contour, and fullness), with each item scored on an ordinal scale from 1 to 4 (very dissatisfied, dissatisfied, satisfied, very satisfied); the FACE-Q Rasch score will be summarized for baseline and change from baseline to month 1 (primary measurement time)

[figure not shown]
Safety Assessments

- AEs, separately for AEs at cheeks, not at cheeks and combined
- Procedural Pain, based on subject assessment on an 11-point scale,
 response distribution by treatment, and paired treatment comparison

of each subject's difference score (-10 to +10)

• Injection Site Responses (ISR), based on subject's 30-day diary, overall and for each of 10 categories (redness, pain after injection, tenderness to touch, firmness, swelling, lumps/bumps, bruising, itching, discoloration and other), response distribution by treatment, separately for presence, severity (none, mild, moderate, severe), number of ISR days (none, 1-3, 4-7, 8-14 and 15 or more), and total duration (none, 1-3, 4-7, 8-14 and 15 or more days)

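### Does the plan need a paired analysis of gel volume and needle use before a non-inferiority result for cannula can be interpreted?

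*SAP*

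**What the plan says.** **Treatment.** Protocol 4.3.1 describes the study treatment as "VOLUMA XC injectable gel injected with a [REDACTED] cannula and an optional [REDACTED"; the name of the optional item is blacked out. The Protocol Synopsis adds: "In the cheek randomized for cannula use, a maximum treatment with cannula should be attempted". It also says both cheeks are treated "with a goal to achieve at least a 1-grade improvement".

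**Volume and blinding.** Protocol 9.1.3 states: "The TI will determine the appropriate volume of VOLUMA XC to inject based on his/her clinical experience"; the rest of that sentence is blacked out. Protocol 4.3.3 states: "The Treating Investigator (TI), study coordinator, and subject will not be blinded to treatment". Only the evaluating investigator is blinded.

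**Exposure tables.** SAP 5.1.2.8, Table 5-11, reports injected volume "By cannula, by needle, and combined across cannula and needle separately for each of cannula and needle cheeks", with descriptive statistics, in the safety population. SAP 5.1.2.9, Table 5-12, counts the device used and the number of injections separately for each cheek. Within that table only injection ease gets a paired difference and interval. Procedural pain also gets one (SAP 4.2, Table 4-1: "response distribution by treatment, and paired treatment comparison").

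**Primary analysis.** SAP 5.1.3.1 uses the paired t-test 95% interval for the cannula-minus-needle difference in MFVDS change at Month 1, and requires an upper limit below 0.5. On subgroups, Protocol 8.4 says: "The primary effectiveness endpoint will be summarized by baseline overall MFVDS score and investigational site". The other visible looks at the primary endpoint are the per-protocol and as-randomized analyses, the two missing-data methods, and an ANOVA on site. None uses volume or needle use.

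**The concern.** The investigator who chooses the volume knows which device is in use and treats toward a target. If cannula delivery were less effective, extra gel or some needle-delivered gel in the cannula cheek could make up the shortfall. The MFVDS comparison would then come out non-inferior for the strategy of cannula plus an optional component, while saying less about cannula delivery itself. The stated objective concerns effectiveness using cannula.

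Volume is the main quantity the investigator can adjust, yet it gets no paired comparison although pain and injection ease do. The interval for a paired volume difference cannot be rebuilt exactly from two separate means and SDs, because it depends on the within-subject correlation. At stake is how a positive result is read: non-inferiority with similar volumes and little needle use supports a stronger statement than non-inferiority with more gel or frequent needle use.

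**Working it through.** The plan gives no figure for volume, its SD, the within-subject correlation or the needle share, so there is nothing of its own to reproduce here. The inputs from the documents are 60 treated subjects (Protocol 5.1) and the margin of 0.5 grade (SAP 5.1.3.1). All other values below are assumptions.

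**1. How much could needle use matter?** Suppose cannula-only treatment is truly worse by the full 0.5, and a share q of cannula cheeks is brought to zero difference by needle use. The mean difference is 0.5(1 − q), and its variance is SD² + q(1 − q) × 0.25. With n = 60 and a noncentral t calculation, the chance of concluding non-inferiority is:

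| SD of paired difference | q = 0 | q = 0.10 | q = 0.25 | q = 0.50 |
|---|---|---|---|---|
| 0.5 | 2.5% | 10.9% | 41.6% | 92.6% |
| 0.75 | 2.5% | 7.2% | 23.0% | 67.3% |
| 1.0 | 2.5% | 5.7% | 15.2% | 45.5% |

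These are not false positives for the strategy under test. They do show that the needle share must be known in order to read the result.

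**2. Would the planned tables show it?** Needle use in the cannula cheek is a within-cheek quantity and needs no pairing. Table 5-11 reports needle-delivered volume in that cheek, and Table 5-12 counts the device used there. A share of 0.25 would be 15 of 60 subjects. Mean needle volume divided by mean total volume in the cannula cheek gives the average needle share v. If effect is linear in volume, total volumes are equal and v is constant, an upper limit of 0.5 for the strategy corresponds to 0.5/(1 − v) for a cannula-only cheek: 0.56, 0.63 or 0.71 at v = 10%, 20% or 30%. A reader can make that conversion from Table 5-11.

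**3. Total volume.** For subjects treated on both cheeks, the mean of the within-subject differences equals the difference of the two cheek means. The point estimate is therefore available. For precision, the SD of the difference is SD × √(2(1 − ρ)), and the half-width is t(0.975, 59)/√60 = 2.001/7.746 = 0.258 times that:

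| Correlation ρ | Half-width (per-cheek SDs) | % of mean, CV 30% | % of mean, CV 50% |
|---|---|---|---|
| 0 | 0.365 | 11.0 | 18.3 |
| 0.5 | 0.258 | 7.7 | 12.9 |
| 0.8 | 0.163 | 4.9 | 8.2 |
| 0.9 | 0.116 | 3.5 | 5.8 |

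The first row needs only the reported SDs, and it is conservative for any non-negative correlation.

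**4. Against the size of a compensating excess.** If effect is linear in volume, a cannula less effective per mL by a fraction d needs 1/(1 − d) − 1 more gel: 11%, 25% or 43% for d = 0.1, 0.2 or 0.3. Excesses of 25% and 43% exceed the zero-correlation half-width at both CVs. An 11% excess is borderline at CV 30%. At CV 50% it is inside the zero-correlation half-width (18.3%) and also inside the paired one at ρ = 0.5 (12.9%). The paired interval adds information there only when the correlation is high (8.2% at 0.8, 5.8% at 0.9).

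**5. Splitting the MFVDS difference by needle use.** If 20% or 30% of subjects had needle use (12 or 18 of 60), the half-widths in that group are t(0.975, 11)/√12 = 0.635 SD and t(0.975, 17)/√18 = 0.497 SD, against 0.258 SD overall. At an SD of 1.0 grade, 0.635 is wider than the whole margin.

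**The case for a change.** The best argument for a change is consistency and low cost. The design is paired, the SAP uses paired intervals for outcomes of less interpretive weight, and volume by device and cheek is already recorded. One phrase in Table 5-11 would supply the missing precision. Step 1 shows that the same conclusion can mean different things.

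Part of this stands. Table 5-11 as written does not give the precision of the within-subject volume difference, and a paired interval would sharpen the picture for modest excesses when the cheeks are highly correlated. It would also be harmless. But pain and injection ease are responses to treatment, while volume is exposure, and describing exposure without inference is ordinary practice. No objective, hypothesis or endpoint requires equal volumes. An analyst who wants the paired interval can produce it from the collected data at any time without affecting the primary conclusion.

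The case for splitting MFVDS by needle use is weaker. The split is made after randomization, on something the investigator chose in response to how the cheek behaved, so cheeks completed with cannula alone may be those that suited it. With perhaps 12 to 18 subjects on one side, the result could mislead as easily as inform.

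What the plan lacks also cannot be settled from the public text. Protocol 8.3.3 is blacked out, and so are parts of the treatment description. SAP 5.1.5, 5.2 and Table 5-17 are not visible, and Protocol 8.4 defers subgroup details to the SAP. Limits on volume or needle use, or further analyses, could be there.

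**Conclusion.** No change is needed. The observation is accurate for the visible text: volume is summarized descriptively, and nothing visible links volume or needle use to MFVDS. It does not follow that a reader is left unable to judge. Tables 5-11 and 5-12 show needle-delivered and total gel in each cheek and the devices used. The mean paired volume difference follows by subtraction, and its uncertainty is bounded at about 11% to 18% of mean volume. That bound assumes 60 subjects treated on both cheeks, per-cheek CVs of 30% to 50% and a non-negative correlation. It is tight enough to reveal a 25% excess.

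The safety population differs from the modified intent-to-treat set only if someone is treated on one cheek alone, so the choice of population matters little. The primary comparison, margin and conclusion are unaffected. A paired volume interval is an optional reporting extra, and the split by needle use offers no reliable gain.
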